5.1.3 Statistical Methods for Additional Objectives

There are no hypotheses. All of the main analyses will be descriptive.

5.1.3.1 Immunogenicity

STAGES I / II

The immune response to each dengue serotype at each time point overall, by baseline dengue serostatus (only in STAGE I) and by age group and country will be assessed descriptively using the following parameters:

- GMT for each serotype (parental strains) at each time point
- GMTR for each serotype (parental strains) 28 days after the second (Group 1 and 2), and third injections (Group 1, 2 and 3), and 28 days after booster (Group 1, 2, and 3) based on the baseline neutralizing Ab titer (see Section 4.4.1.4 for baseline dengue assessment for each group):
 - 28 days after second injection: V04/V01 (Group 1) & V04/V03 (Group 2)
 - 28 days after third injection: V06/V01 (Group 1), V06/V03 (Group 2) & V06/V05 (Group 3)
 - 28 days after booster injection: V10/V01 (Group 1), V10/V03 (Group 2) & V10/V05 (Group 3)
- GMTR for each serotype (parental strains) 28 days after booster (Group 1, 2, and 3) based on the 28 days post third and pre-booster injection neutralizing Ab titer:
 - Based on 28 days post third injection: V10/V06 (for Groups 1, 2 and 3)
 - Based on pre-booster: V10/V07 (for Groups 1, 2 and 3)
- Number and percentage of subjects with dengue neutralizing Ab titer ≥ 10 (1/dil) (parental strains) at each time point against each serotype
- Number and percentage of subjects with dengue neutralizing Ab titer ≥ 10 (1/dil) (parental strains) at each time point against at least one, two, three, or the four dengue serotypes.
- Number and percentage of subjects \geq various titer thresholds (1/dil) for at least 1, 2, 3, or 4 serotypes with parental dengue virus strains at each time point.
- Distribution of titers against each of the 4 serotypes at each time point and corresponding RCDC
- Number and percentage of subjects who converted (based on pre- and 28 days post-booster time points)
- GM at baseline and 28 days after injection 3 for each serotype in subjects belonging to Groups 1, 2 and 3 (aggregate) who are seropositive at baseline and AUC-MB at baseline and 28 days after injection 3 for the average of the four serotypes, by age strata (9-16 years of age, 17-45 years of age, and 45-50 years of age), overall and by country.
- GM at baseline and 28 days after injection 3 for each serotype in subjects belonging to Group 1 who are seropositive at baseline, and AUC-MB at baseline and 28 days after injection 3 for

the average of the four serotypes, by age strata (9-16 years of age, 17-45 years of age, and 46-50 years of age), overall and by country.

- GM at baseline and 28 days after injection 3 for each serotype in subjects belonging to Group 2 who are seropositive at baseline, and AUC-MB at baseline and 28 days after injection 3 for the average of the four serotypes, by age strata (9-16 years of age, 17-45 years of age, and 46-50 years of age), overall and by country.
- GM at baseline and 28 days after injection 3 for each serotype in subjects belonging to Group 3 who are seropositive at baseline, and AUC-MB at baseline and 28 days after injection 3 for the average of the four serotypes, by age strata (9-16 years of age, 17-45 years of age, and 46-50 years of age), overall and by country.
- GM at pre-booster and 28 days post-booster for each serotype in subjects belonging to Groups 1a, 2a and 3a (aggregate) /1b, 2b and 3b (aggregate) who are seropositive at baseline and AUC-MB at pre-booster and 28 days post-booster for the average of the four serotypes, by age strata (9-16 years of age, 17-45 years of age, and 46-50 years of age), in Colombia and by 1a/1b, 2a/2b, 3a/3b separately.

Additionally, the number and percentage of subjects immune or non-immune to dengue, and JE or YF status at baseline overall and by age group and country.

Between groups comparisons at 28 days and 1 year after injection 3 (ie, Group 2 vs Group 1, Group 3 vs Group 1) in STAGE I will be described using GMR at each time point for each serotype, in subjects seropositive at baseline.

Between age strata comparisons at baseline and 28 days after injection 3 (9-16 years vs 17-45 years vs 46-50 years) in STAGE I will be described using GMR (9-16y/17-45y; 9-16y/46-50y; 17-45y/46-50y) for each serotype, in subjects seropositive at baseline. Between age strata comparisons at pre-booster and 28 days post-booster (9-16 years vs 17-45 years vs 46-50 years) in STAGE II will be described using GMR (9-16y/17-45y; 9-16y/46-50y; 17-45y/46-50y) for each serotype, in subjects seropositive at baseline. Exploratory assessment of non-inferiority between age strata will be based on upper bound of 95% CI of the GMR being <2.

Between groups comparisons within the year of the booster (i.e., Group 2a vs Group 1a, Group 3a vs Group 1a, Group 2b vs Group 1b and Group 3b vs. Group 1b) will be described using GMR for each serotype 28 days after booster based on subjects seropositive at baseline.

5.1.3.1.1 Analysis adjusting for baseline or pre-booster neutralizing Ab levels

Analysis of covariance (ANCOVA) also will be used to compare the mean response of neutralizing Ab levels against each dengue virus serotype 28 days after injection 3 between age strata adjusting for baseline neutralizing Ab levels against each dengue virus serotype based on the least squares means, in subjects seropositive at baseline.

For each serotype, the following model will be considered:

$$\text{Log}_{10} \text{ titer}_i = \log_{10} \text{ baseline}_i + \text{country} + \text{age strata}_i$$

Where:

- $titer_i$ is the 28 days after injection 3 titer value for each subject
- $baseline_i$ is baseline titer value for each subject. Sample collected at V01 (BL1), V03 (BL2, or BL1 if BL2 is unavailable) and V05 (BL4, or BL2 if BL4 is unavailable, or even BL1 if BL2 is unavailable) will be used as baseline for Group 1, Group 2 and Group 3 respectively.
- $country$ is the country for each subject
- $age\ strata_i$ is the age strata for each subject

Before applying the above ANCOVA model, the interactions will be assessed using the following model:

$$\log_{10} titer_i = \log_{10} baseline_i + age\ strata_i + country + \log_{10} baseline_i \times age\ strata_i + age\ strata_i \times country$$

Analysis of covariance (ANCOVA) will be used to compare the post-booster mean response of neutralizing Ab levels against each dengue virus serotype of two groups (i.e., Group 2a vs Group 1a and Group 3a vs Group 1a in Year 1, Group 2b vs Group 1b and Group 3b vs. Group 1b in Year 2) adjusting for the pre-booster neutralizing Ab levels against each dengue virus serotype based on the least squares means (LSMEANS), in subjects seropositive at baseline in Colombia. The confidence intervals and p-values from Type III sums of squares may also be presented. A Bonferroni adjustment will be used to control for multiplicity.

For each serotype, the following model will be considered:

$$\log_{10} titer_i = \log_{10} pre-booster_i + group_i + age\ group_i$$

Where:

- $titer_i$ is the post-booster titer value for each subject
- $pre-booster_i$ is pre-booster titer value for each subject
- $group_i$ is Group 1a, Group 1b, Group 2a, Group 2b, Group 3a, and Group 3b for each subject
- $age\ group_i$ is the age group for each subject

Before applying the above ANCOVA model, the interactions will be assessed using the following model:

$$\log_{10} titer_i = \log_{10} pre-booster_i + group_i + age\ group_i + \log_{10} pre-booster_i \times group_i + group_i \times age\ group_i$$

Analysis of covariance (ANCOVA) also will be used to compare the mean response of neutralizing Ab levels against each dengue virus serotype 28 days post-booster between age strata adjusting for the pre-booster neutralizing Ab levels against each dengue virus serotype based on the least squares means, in subjects seropositive at baseline, in Colombia.

For each serotype, the following model will be considered:

$$\log_{10} titer_i = \log_{10} pre-booster_i + age\ strata_i$$

Where:

- $titer_i$ is the 28 days post-booster titer value for each subject

- pre-booster_i is pre-booster titer value for each subject.
- age strata_i is the age strata for each subject

Before applying the above ANCOVA model, the interactions will be assessed using the following model:

$$\text{Log}_{10} \text{ titer}_i = \text{log}_{10} \text{ pre-booster}_i + \text{age strata}_i + \text{log}_{10} \text{ pre-booster}_i \times \text{age strata}_i$$

5.1.3.2 AIT Subset

The analyses for AIT subset are based on the following:

Dengue PRNT (at V01, V06, V07, V08, V09 and V10): neutralizing Ab levels against each of the four parental dengue virus strains as determined by PRNT.

CMI responses (at V01, V07, V08, V09 and V10):

- Cytokine secreting CD4 and CD8 T cells count (at V01, V07, V08, V09 and V10)

Note: The raw individual results will not be directly described in the analysis: the results of all stimulations will be corrected with the corresponding medium result. The detailed calculation is below:

For envelope (ENV) CYD 1, ENV CYD 2, ENV CYD 3, ENV CYD 4, NS3 peptide pools from YF 17D and DEN, and positive control, the medium (MED) = value of the negative control medium.

Therefore, the following corrected endpoints will be used:

- Before vaccination: $X_{D0} - MED_{D0}$ where X is the value of ENV CYD 1, ENV CYD 2, ENV CYD 3, ENV CYD 4, positive control or NS3 peptide pools from YF 17D and DEN, etc.
- 28 days after vaccination: $X_{D28} - MED_{D28}$,
- 12 months after vaccination: $X_{M12} - MED_{M12}$,
- Change from baseline endpoints (ratio): $(X_{D28} - MED_{D28}) / (X_{D0} - MED_{D0})$ and $(X_{M12} - MED_{M12}) / (X_{D0} - MED_{D0})$.
- Change from D28 endpoints (ratio): $(X_{M12} - MED_{M12}) / (X_{D28} - MED_{D28})$.
- T cell subpopulation (naïve, effector, central and terminally differentiated memory T cells) count (at V01, V07, V08, V09 and V10)

Note: Naïve T cells are defined as CD45RA+ and CCR7+, effector memory T cells defined as CD45RA- and CCR7-, central memory T cells defined as CD45RA- and CCR7+, and terminally differentiated memory T cells as CD45RA+ and CCR7-.

- No corrected value will be used for the subpopulation analyses. Only the raw value of the medium, ENV CYD1, ENV CYD 2, ENV CYD 3, ENV CYD 4, positive control or NS3 peptide pools from YF 17D and DEN will be summarized.
- Cytotoxic T cell effector markers (at V01, V07, V08, V09 and V10)

Note: The functional markers are including IFN γ , TNF α , IL-2, MIP-1 β and CD107a for CD3+ CD8+ T cells, and have one more marker CD154 for CD3+ CD4+ T cells. The

cytotoxic T cell will be also summarized for activated cells, simple positive cells, double positive cells, triple positive cells and more than triple positive cells. The definition for different cells are:

- Activated cells: Positive for at least one of the following markers IFN γ /TNF α /IL-2/MIP-1 β /CD107a for CD3+ CD8+ cells and IFN γ /TNF α /IL-2/MIP-1 β /CD107a/CD154 for CD3+ CD4+ cells
- Simple positive cells: Activated cells which express 1 of the following markers IFN γ /TNF α /IL-2/MIP-1 β /CD107a for CD3+ CD8+ cells and IFN γ /TNF α /IL-2/MIP-1 β /CD107a/CD154 for CD3+ CD4+ cells
- Double positive cells: Activated cells which express 2 of the following markers IFN γ /TNF α /IL-2/MIP-1 β /CD107a for CD3+ CD8+ cells and IFN γ /TNF α /IL-2/MIP-1 β /CD107a/CD154 for CD3+ CD4+ cells
- Triple positive cells: Activated cells which express 3 of the following markers IFN γ /TNF α /IL-2/MIP-1 β /CD107a for CD3+ CD8+ cells and IFN γ /TNF α /IL-2/MIP-1 β /CD107a/CD154 for CD3+ CD4+ cells
- More than triple positive cells: Activated cells which express 3 of the following markers IFN γ /TNF α /IL-2/MIP-1 β /CD107a for CD3+ CD8+ cells and IFN γ /TNF α /IL-2/MIP-1 β /CD107a/CD154 for CD3+ CD4+ cells

In addition, the number of responders to the ICS test by stimulation will be computed. To be considered as responders the two following conditions must be filled:

$$\frac{X_{post-booster} - MED_{post-booster}}{X_{D0} - MED_{D0}} \geq 2$$

$$[X_{post-booster} - MED_{post-booster}] - [X_{D0} - MED_{D0}] \geq 0.05\%$$

- The post-booster visits here are D28 and M12
- Ex vivo B cells (plasmablast) count (measured by ELISPOT) (at V01, V07, V08 and V09)
- Number of antibody secreting cells (ASC) for each of the four specific parental dengue virus strains IgG and the total IgG will be summarized.
- Memory B cells count (measured by ELISPOT) (at V01, V07, and V10)

Note: Antibody secreting cells (ASC) for each of the four specific parental dengue virus strains IgG and the total IgG will be summarized. In addition, for each of the four specific parental dengue virus strains IgG, the ratio will be also calculated. The ratio (%) can be obtained by:

$$\text{Ratio} = \frac{\text{ASC for CYD1/2/3/4 IgG}}{\text{ASC for Total IgG}} \times 100\%$$

Ab specificity and affinity maturation:

- The neutralizing Abs in the wide-type dengue parental strains (DENV) depleted, BSA-control depleted sera and whether the response is homotypic for each of the four parental dengue virus strains will be assessed (at V01, V06, V07, V08, V09 and V10).

Note: Undepleted is defined as BSA-control depleted sera and depleted is DENV depleted samples. Homotypic response is defined as a neutralizing antibody titer above 20 (1/dil) following DENV depletion.

- Serotype-specific affinity (KA, nM⁻¹) and Ab concentration (µg/mL) for each of the four parental dengue virus strains will be measured (at V01, V06, V07, and V10).

All the analyses will be descriptive at each available time point by treatment subgroups (Group 1a/1b/2a/2b/3a/3b), by subgroups in Y1 (Group 1a/2a/3a), by subgroups in Y2 (Group 1b/2b/3b) and by treatment groups (Group 1/2/3)..

- For categorical data, the number and percentage of subjects above or equal to the LLOD, and the 95% CI of the percentage of the subjects.
- For continuous data, Log10: mean and standard deviation; geometric mean, 95% CI of the geometric mean and quartiles, minimum and maximum value

As this objective is exploratory, other analyses might be performed.

Note: A total of 60 subjects (10 subjects in each of 6 subgroups) who consent to participate in additional immunological testing will also be included in a specific subset (AIT subset). The 1:1 ratio and 10 subjects per subgroup is unlikely to hold as only subjects dengue seropositive at baseline will be eligible to booster injection.

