9.3 Additional Endpoints and Assessment Methods

9.3.1 Immunogenicity

9.3.1.1 Immunogenicity Endpoints

STAGE I:

- Neutralizing Ab titers against each dengue virus serotype at all STAGE I time points
- Neutralizing Ab titers against FVs at baseline prior to first injection of CYD dengue vaccine (JE in the Philippines, YF in Colombia)

STAGE II:

- Neutralizing Ab titers against each dengue virus 28 days post booster injection (Y1 for subgroup a and Y2 for subgroup b)

AIT Subset Only:

The immune response against the 4 dengue serotypes elicited by the boosting dose of dengue vaccine will be assessed by the measurement of neutralizing antibodies, to include:

- 1) Neutralizing Ab response
 - a. Neutralizing Ab levels against each of the 4 parental dengue virus strains immediately prior to and at 7, 14, and 28 days post-booster injection
- 2) Ab specificity and affinity maturation
 - a. Heterotypic and homotypic serotype-specific neutralizing Ab responses will be assessed qualitatively immediately prior to and 28 days post-injection 3 (STAGE I); and immediately prior to and at 28 days post-booster injection as a priority, and at 7 and 14 days post-injection if necessary (STAGE II). Homotypic Abs for individual serotypes will be defined based on values above lower limits of quantitation for the neutralizing titer and % of Ab remaining following depletion.
 - b. Serotype-specific affinity (K_D , nM) and Ab concentration ($\mu\text{g/mL}$) will be measured against the parental wild-type strains in the sera immediately prior to and at 28 days post-injection 3 (STAGE I) and immediately prior to and at 28 days post-booster injection (STAGE II).
- 3) CMI responses

The specific B and T immune response against the 4 dengue serotypes elicited by the CYD dengue vaccine booster will be assessed by ELISPOT or flow cytometry, using intracellular staining and phenotyping

- a. T-cell response:
 - Cytokine secreting CD4 and CD8 T cells count immediately prior to the primary dose schedules (STAGE I) and immediately prior to and 7, 14, and 28 days after the Year 1 and Year 2 booster dose for a subset of subjects in Groups 1, 2, and 3.
 - T-cell subclasses (naïve, effector, central and terminally differentiated memory T cells) count immediately prior to the primary dose schedules (STAGE I), and

immediately prior to and 7, 14, 28 days after the Year 1 or year 2 booster dose for a subset of subjects in Groups 1, 2, and 3.

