2.3 Additional Objectives

Immunogenicity

STAGE I:

- To describe the neutralizing Ab response of flavivirus (dengue/Japanese Encephalitis [JE] in the Philippines, and dengue/YF in Colombia) serological status by age group and country at baseline in all 3 groups.
- To describe the neutralizing Ab response to each dengue serotype at each available time point by baseline serostatus in all 3 groups.
- To compare the immune response elicited against each dengue serotype by the CYD dengue vaccine given as a 2-dose schedule (Group 2) or a 1-dose schedule (Group 3) and given as a 3-dose schedule (Group 1) at 28 days after last injection, in subjects seropositive at baseline, in terms of GMR.
- To compare the immune response elicited against each dengue serotype by the CYD dengue vaccine given as a 2-dose schedule (Group 2) or a 1-dose schedule (Group 3) and given as a 3-dose schedule (Group 1) at 1 year after last injection in subjects seropositive at baseline, in terms of GMR.

STAGE II:

Booster Dose at One and Two Years

- To describe the neutralizing Ab response to each dengue serotype 28 days after a booster injection

One Year Booster:

- To describe the immune response elicited against each serotype 28 days after administration of a booster dose of CYD dengue vaccine 1 year after the last primary series vaccination in a 2-dose schedule (Group 2) or 1-dose schedule (Group 3) when compared to a 3-dose schedule (Group 1)

Two Year Booster:

- To describe the immune response elicited against each serotype 28 days after administration of a booster dose of CYD dengue vaccine 2 years after the last primary series vaccination in a 2-dose schedule (Group 2) or 1-dose schedule (Group 3) when compared to a 3-dose schedule (Group 1)

STAGE I and STAGE II Additional Immunological Tests (AIT) Subset Only:

- To describe dengue neutralization Ab levels (exploration of Ab response kinetics), Ab specificity and affinity maturation in a subset of subjects (N=60) in all groups (Ratio between subgroups 1:1 = 10 subjects per subgroup).
- To describe cell-mediated immune (CMI) responses at Day 0 [STAGE I] and at 0, 7, 14, 28 days post-booster dose (Y1 and Y2) in this subset of subjects participating in all groups

Note: It is to be noted that the 1:1 ratio per subgroup and N=60 are unlikely to hold as only subjects dengue seropositive at baseline will be eligible to booster injection.

3 Description of the Overall Trial Design and Plan

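### The ICS responder rule does not tie D0, D28 and M12 to actual CMI samples: its reference may be V01 rather than the pre-booster sample, and M12 is not a post-booster visit

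*SAP*

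**What the plan says.** SAP 5.1.3.2 introduces the count with "In addition, the number of responders to the ICS test by stimulation will be computed" and continues: "To be considered as responders the two following conditions must be filled". Both conditions set a medium-corrected value labelled post-booster against the corrected D0 value. The ratio must be at least 2 and the difference at least 0.05%. Neither condition contains a pre-booster term. The rule then adds: "The post-booster visits here are D28 and M12".

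The only explanation of D0 in that section is "Before vaccination: $X_{D0} - MED_{D0}$ where X is the value of ENV CYD 1". Which vaccination is meant is not stated. M12 is explained in the same way, as 12 months after an unspecified vaccination.

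The purpose is clearer. Protocol 9.3.1.1 describes the B- and T-cell response "elicited by the CYD dengue vaccine booster will be assessed by ELISPOT or flow cytometry". The CMI objective in SAP 2.3 reads "To describe cell-mediated immune (CMI) responses at Day 0 [STAGE I] and at 0, 7, 14, 28 days post-booster dose (Y1 and Y2". SAP 5.1.3.2 lists CMI samples at V01, V07, V08, V09 and V10 only. SAP Table 5.1 plans the number and percentage of responders with 95% CIs.

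**The concern.** To describe what a booster adds, the reference should be the sample taken just before it. V01 is about 24 months before the booster in subgroup a (V05 = V01 + 12 months; Year 1 V07 = V05 + 12 months) and about 36 months before it in subgroup b. In that interval Groups 1, 2 and 3 receive 3, 2 and 1 CYD doses in endemic countries. With V01 as reference, anything gained from the primary series or natural infection and still present at V07 counts towards the responder definition, so the rate could not be read as a booster effect.

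Two programmers could also read D0 and M12 differently and produce different responder tables from the same data.

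**Working it through.** The documents give no expected responder rate, so there is no figure to reproduce. The check has three parts.

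**1. Which sample is D0?**

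| Points to V01 | Points to V07 (pre-booster) |
|---|---|
| SAP 3.2 schedules injections at D0, D180 and D365 | Protocol Tables S3 and 5.4 label the Stage II pre-booster row D0 (they label the pre-injection 1 row D0 as well) |
| SAP 2.3 lists Day 0, tagged Stage I, apart from day 0 of the booster | Protocol 9.3.1.2.2 uses D0 and D28 on the booster clock for affinity |
| SAP 5.1.3.2 calls the ratio to D0 a change from baseline; SAP 5.1.3.1 keeps baseline and pre-booster ratios apart | D28 in the rule can only be V10, because no CMI sample follows a primary injection by 28 days |

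V01 is the better-supported reading within the SAP. It is not settled.

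**2. Which sample is M12?**

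- Counted from V01, month 12 is V05, which has no CMI sample.
- Counted from the booster, there is no CMI sample at 12 months, and follow-up ends at 6 months (SAP 3.2).
- Counted from the last primary injection, it is Year 1 V07 (V05 + 12 months). In subgroup a this is the pre-booster sample; in subgroup b it is a year before the booster.

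So no reading makes M12 post-booster. If D0 is V07 and M12 is Year 1 V07, the M12 ratio in subgroup a is a sample divided by itself: ratio 1, difference 0, never a responder.

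**3. What does the choice of reference do?**

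Let P be the corrected post-booster value and R the corrected reference. A responder needs P/R ≥ 2 and P − R ≥ 0.05. Take an illustrative subject with 0.05% at V01, 0.15% at V07 and 0.15% at V10, so that the booster changed nothing:

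- R = V01: 0.15/0.05 = 3 and 0.15 − 0.05 = 0.10. Responder.
- R = V07: 0.15/0.15 = 1 and 0.15 − 0.15 = 0. Not a responder.

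A simulation of V10 with no booster effect (200,000 draws per setting) gives a range. All inputs are assumptions: lognormal values, median corrected V01 frequency 0.02% or 0.05%, between-subject SD 0.3 log10, assay SD 0.1 or 0.2 log10, and a lasting fold rise F at V07. Each cell shows the result for assay SD 0.1, then 0.2.

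| Median at V01 | F | Responders, V01 reference | Responders, V07 reference |
|---|---|---|---|
| 0.02% | 1 | 0.1%, 2.0% | 0.1%, 2.0% |
| 0.02% | 2 | 10.6%, 16.7% | 0.5%, 5.8% |
| 0.02% | 3 | 36.2%, 36.3% | 0.8%, 8.6% |
| 0.02% | 5 | 72.4%, 66.3% | 1.3%, 11.8% |
| 0.05% | 1 | 0.7%, 7.4% | 0.7%, 7.3% |
| 0.05% | 2 | 33.1%, 37.4% | 1.2%, 11.6% |
| 0.05% | 3 | 74.5%, 62.9% | 1.5%, 13.1% |
| 0.05% | 5 | 96.3%, 87.3% | 1.6%, 14.0% |

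For F from 2 to 5 the range is 10.6% to 96.3% against V01 and 0.5% to 14.0% against V07. With no lasting rise (F = 1) the two references agree.

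**The case against.** The strongest reply is that D0 belongs to one series with D28, and D28 must be V10. A series on the booster clock would make D0 the V07 sample, which is how the protocol labels it for this subset. The D28 comparison would then already be the right one. This stands as a real alternative reading. A reader might infer that the rule definitely compares with the sample before the primary series and so credits older responses to the booster; the documents do not support that as a fact. The alternative reading does not rescue M12, and it leaves D0 undefined in the analysis plan.

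A second reply is that the SAP speaks of responders to the ICS test, not to the booster, and that comparison with a pre-vaccination sample is a planned convention: SAP 5.1.3.1 schedules PRNT ratios to baseline (V10/V01 for Group 1). That is fair, but the same section lists V10/V07 separately, and PRNT seroconversion (SAP 4.4.1.2) uses the pre-booster titer. The ICS rule has no such second comparison.

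A third reply is that little depends on the count. That stands. The AIT analyses are descriptive at each available time point, V07 and V10 included, and no hypothesis test or sample size uses the responder count.

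**Conclusion.** The rule as printed cannot be run without guessing. D0 is ambiguous between V01 and V07, with V01 the more natural reading in the SAP, and M12 matches no post-booster CMI sample. If V01 is used, responses present before the booster satisfy both conditions with no booster effect. That conclusion follows from the two conditions alone.

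The size does not. No document gives ICS frequencies, persistence or assay variance, so the simulated rates illustrate the mechanism and do not predict the trial's results. A reader might also infer that Groups 1, 2 and 3 must show different responder rates even if the booster did the same in each. That would require persistence of the cellular response to differ by number of primary doses, which the documents do not report.

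The point is minor: an exploratory, descriptive endpoint in at most 60 subjects, fewer after seronegative subjects leave the subset. It is still worth correcting because responder percentages with confidence intervals are a planned output.

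**What to change.** In SAP 5.1.3.2, write both responder conditions by visit:

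- Reference: the corrected V07 pre-booster value, from BL6 (Year 1) in subgroup a and BL10 (Year 2) in subgroup b.
- Post-booster visit: V10, with V08 and V09 added if day 7 and day 14 responders are wanted.
- Delete M12 from the list of post-booster visits.
- Report any V01-based ratio separately, labelled as the cumulative response since before the primary series.

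Changing the reference alone is not enough, because leaving M12 in place would compare V07 with itself in subgroup a and, in subgroup b, compare an earlier sample with a later reference.

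The cost is SAP wording and table programming. The V07 to V10 CMI samples are already scheduled, and no hypothesis test, sample size or visit changes.
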